5.3.2 Method

Randomisation will be carried out electronically using an on-line system managed by the ICTU Clinical Data Systems Team. We will use minimisation (with 10% random allocation) to achieve

Title: COLLABORATE	EDGE No: 181495	Sponsor: Imperial College London	Version: 3.0; 09/01/2026
---------------------------	---------------------------	--	---------------------------------

balance between the number of babies in each treatment group over important, well-recognised prognostic factors [neonatal network (N=13); gestational age category (<26w; >=26w); severe growth restriction (<10% centile; >=10% centile based on standard criteria)]. Multiple births will be randomised individually in keeping with our feasibility study (12), other feeding trials (28), and parent focus group advice.

5.4 Procedures and evaluations

There will be no research-related procedures or evaluations except for infants participating in: the embedded mechanistic sub-study, who will be invited for brain MRI which is a well-established procedure and from whom serial stool samples will be obtained.

Title: COLLABORATE	EDGE No: 181495	Sponsor: Imperial College London	Version: 3.0; 09/01/2026
---------------------------	---------------------------	--	---------------------------------

5.5 Schedule of assessments

Timepoint → Assessment ↓	On admission to neonatal care	28 days postnatal age	34 weeks postmenstrual age	36 weeks postmenstrual age	Discharge	37-44 weeks postmenstrual age	2 years corrected for prematurity (23.5–27.5 months)
Eligibility	X						
Consent	X						
Randomisation*	X						
Highest recorded serum urea, creatinine, alkaline phosphatase					X		
Clinical endpoints from NNRD data		X	X	X	X		
Additional clinician recorded endpoints					X		
MRI**						X	
Stool sample**	X	X	X			X	
PARCA-R***							X
Adverse Reactions		X	X		X	X	

Title: COLLABORATE	EDGE No: 181495	Sponsor: Imperial College London	Version: 3.0; 09/01/2026
---------------------------	---------------------------	--	---------------------------------

** When the participant meets the relevant inclusion/exclusion criteria for each randomisation*

*** Only participants in the mechanistic sub-study*

**** To be completed using the digital PARCA-R where possible (facilitated through ICTU)*

Title: COLLABORATE	EDGE No: 181495	Sponsor: Imperial College London	Version: 3.0; 09/01/2026
---------------------------	---------------------------	--	---------------------------------

5.6 Safety considerations

5.6.1 Nutritional supplements

We recommend that infants randomised to the “no routine fortification” arm receive routine oral phosphate supplements to protect against metabolic bone disease. Other supplements including vitamins to be provided in accordance with the policies of the participating neonatal unit.

5.6.2 Faltering growth

Clinicians may consider discretionary use of fortifier in babies participating in randomisation 2 should there be evidence of growth faltering and non-nutritional causes have been excluded; guidance will be provided in the study manual.

Clinicians considering rescue fortification are advised to discuss this with the clinical CI or delegate. Rescue fortification will be documented in the eCRF and factored into analyses.

5.6.3 MRI

The MRI scanner makes a loud knocking noise, so earmuffs are used to prevent noise discomfort and encourage infants to sleep. We will use established procedures that ensure infant safety and physiological stability during imaging (29). The infant will have continuous monitoring of vital signs (heart rate and oxygen saturation) with an electronic monitor. The attending clinician will record observations every 5 minutes until 1 hour after the infant has woken up, and the scan will be stopped if there are any abnormalities in monitoring. Full neonatal resuscitation facilities are available on site. Standard Operating Procedures for ensuring safety in the MRI environment in place in the Edinburgh Imaging facility will be followed.

5.7 Follow-up

No research-related follow-up visits are required. Age 2-year cognitive and language outcomes will be obtained using the parent-completed PARCA-R in accordance with NICE recommendation (30). A digital version of the PARCA-R will be made available to clinical teams should they wish to use this in which case parents will be registered to do so at neonatal unit discharge (31).

5.8 Laboratory evaluations

No research-related laboratory evaluations are required for the majority of participants. Maximum serum urea, creatine, and alkaline phosphatase will be recorded from routine blood results during time on the neonatal unit.

For participants recruited at the Royal Infirmary of Edinburgh, consent will be sought for collection of serial stool samples at enrolment and each week until 34 weeks postmenstrual age. An additional sample will be collected at the time of the MRI scan if the baby is enrolled to both aspects of the mechanistic sub-study. Between 7 and 14 stool samples will be collected depending on birth gestational age.

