2.4.2 Secondary

Assessed at 34 weeks postmenstrual age

- Survival
- Surgical NEC
- Spontaneous Intestinal Perforation

Assessed at 36 weeks postmenstrual age

- Bronchopulmonary dysplasia

Assessed at postnatal age 28 days

- Survival

Assessed at neonatal unit discharge (or death)

- Survival
- Surgery for NEC or NEC related condition after 34 weeks postmenstrual age
- Medical NEC
- Age in days to achieve an enteral intake of 150 ml/kg/day
- Treated retinopathy of prematurity

Title: COLLABORATE	EDGE No: 181495	Sponsor: Imperial College London	Version: 3.0; 09/01/2026
---------------------------	---------------------------	--	---------------------------------

- Severe brain injury
- Any diagnosis of milk-curd obstruction
- Length of neonatal unit stay
- Number of episodes of bacterial or fungal bloodstream infection
- Number of episodes of bacterial or fungal cerebrospinal fluid infection
- Number of episodes of bacterial or fungal urinary tract infection
- Number of days of antibiotic treatment
- Number of days on parenteral nutrition
- Number of days nil by mouth
- Weight, length, and head circumference Z-scores
- Change from birth in Z-scores for weight, length, and head circumference
- Any breast feeding (suckling at breast)
- Exclusive breast feeding (suckling at breast)
- Receiving any expressed Own Mother's Milk
- Receiving exclusive expressed Own Mother's Milk
- Maximum serum urea, creatine, and alkaline phosphatase
- Health resource use

Assessed at neonatal unit discharge (or death) in babies with NEC surgery

- Drain insertion prior to surgery (yes/no)
- Diagnosis of short bowel syndrome (yes/no)
- Diagnosis of intestinal failure-associated liver disease (yes/no)
- Length of bowel resected (cm)
- Primary surgical procedure (ileostomy; colostomy; end-to-end anastomosis)
- Number of re-operations (excluding primary operation)

Assessed at age 2-years corrected for prematurity

- Survival without moderate-severe cognitive-language impairment
- Survival
- Moderate-severe cognitive-language impairment
- Cognitive sub-score
- Language sub-score
- Gross motor function
- Hearing impairment
- Vision impairment

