5.3 Randomisation: timing and method

5.3.1 Timing

Babies may participate in either or both randomisations; see Flow Chart, Appendix 1.

Randomisation 1 to pHDM or Preterm Formula, will occur when the attending clinician decides a supplemental feed is required because the volume of Own Mother's Milk is insufficient.

Randomisation 2, to routine fortification or no routine fortification, will occur when the baby is receiving between 60-120 ml/kg/day of human milk feeds (Own Mother's Milk and/or pHDM). By "fortification" we mean immediate or incremental increase to "full strength fortification" according to neonatal unit practice. We refer to "no routine fortification" because rescue fortification is permitted (see section 5.6.2).

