9.5 Ancillary data capture

Requirements for data other than those obtained from the NNRD are minimal (consent; randomisation; recruiting site; protocol deviations/violations; SAR; withdrawals; clinical information; maximum alkaline phosphatase, urea, and creatinine during in-patient stay as indices of metabolic bone disease, protein intake, and renal function, respectively) and will be obtained through Electronic Data Capture (EDC) using a dedicated eCRF system (OpenClinica).

Data will be entered into the EDC system by trained site personnel. All data recorded in the eCRF will be signed off by the Investigator or his/her appropriate designee. All changes made following initial submission of data will have an electronic audit trail with a date. Details of procedures for eCRF completion will be provided in a study manual.

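### Maximum urea, creatinine and alkaline phosphatase are taken over the whole neonatal stay, so a value from before randomisation can be the recorded outcome and dilute a true effect

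*Protocol*

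**What the plan says.** The protocol lists "Maximum serum urea, creatine, and alkaline phosphatase" as a secondary endpoint assessed at neonatal unit discharge or death (section 2.4.2), with no start to the window. Two other sections supply one:

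- Section 5.8: "Maximum serum urea, creatine, and alkaline phosphatase will be recorded from routine blood results during time on the neonatal unit".
- Section 9.5, on eCRF data: "maximum alkaline phosphatase, urea, and creatinine during in-patient stay as indices of metabolic bone disease, protein intake, and renal function, respectively".

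The schedule in section 5.5 has one row, "Highest recorded serum urea, creatinine, alkaline phosphatase", marked only at discharge. No section asks for the date of the highest value or schedules a value at or before randomisation.

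Both randomisations come later than the opening of that window (section 5.3.1). Randomisation 1 "will occur when the attending clinician decides a supplemental feed is required". Randomisation 2 "will occur when the baby is receiving between 60-120 ml/kg/day of human milk feeds". Section 7.3 adds that randomisation 2 follows randomisation 1. Babies who have already had donor milk or formula are excluded from randomisation 1 (4.2.1.2), and babies who have already had fortifier are excluded from randomisation 2 (4.2.2.2).

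Elsewhere the protocol does open its windows at randomisation: safety reporting in section 6.7 and resource use in section 7.9.

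**The concern.** An outcome should be something the allocated treatment could have changed. Because of the exclusions, every blood result before a given randomisation comes from a baby not yet exposed to that comparison's feeds. If such a result is the highest of the stay, it becomes the baby's recorded outcome and says nothing about the feed.

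The three analytes are there for safety. Section 9.5 ties urea to protein intake, creatinine to renal function and alkaline phosphatase to bone disease. Section 1.4 raises the possibility that routine fortification gives too much protein, with renal health among the things at risk. Section 2.4.2 lists no other renal measure. A marker that loses sensitivity in this setting errs towards reassurance. The exposed period also tends to be longer for randomisation 2, the comparison that tests fortification, because feeds must first be advanced.

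**Working it through.** The protocol gives no effect size, standard deviation or power for these analytes, so there is no figure of its own to reproduce. The check is how far a whole-stay maximum weakens a true effect.

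**Formula.** Let X be a baby's highest value before randomisation, Y the highest value after it without the intervention, and d a common shift in Y caused by the intervention. The recorded outcome is Z = max(X, Y + d). Then dE[Z]/dd = P(Y + d > X). At d = 0 this equals 1 - p, with p = P(X > Y). For small d the observed mean difference is therefore about d(1 - p), whatever the distributions. The sample size needed for the same power grows by about 1/(1 - p)².

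**Inputs for an illustration**

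- Babies per arm: 1084 (section 7.2.1), less 2% missing: 1084 × 0.98 = 1062. Section 7.4 shows nearly the same for randomisation 2: 2126/2 = 1063.
- Two-sided alpha 0.05.
- d = 0.15 SD: an assumption, not in the protocol.
- p: not in the protocol, so shown as a range.

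**Power**, with SD held at 1, is Φ(0.15 × (1 - p) × √(1062/2) - 1.96), where √531 = 23.04 and 0.15 × 23.04 = 3.456.

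| p | share of effect kept | 3.456 × (1 - p) | power | sample size multiplier |
|---|---|---|---|---|
| 0 | 1.00 | 3.456 | 0.93 | 1.00 |
| 0.2 | 0.80 | 2.765 | 0.79 | 1.56 |
| 0.4 | 0.60 | 2.074 | 0.55 | 2.78 |
| 0.5 | 0.50 | 1.728 | 0.41 | 4.00 |
| 0.6 | 0.40 | 1.382 | 0.28 | 6.25 |
| 0.8 | 0.20 | 0.691 | 0.10 | 25.0 |

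**Simulation check.** X and Y were drawn as normal with SD 1 and correlation 0, 0.4 or 0.7. The mean of X was moved from 2 SD below to 2 SD above that of Y, again with d = 0.15 SD.

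| share of maxima before randomisation | share of effect kept | power (0.93 without dilution) |
|---|---|---|
| 8% or less | 93-100% | 0.92-0.93 |
| 10-24% | 78-92% | 0.87-0.90 |
| 50% | 52-54% | 0.50-0.59 |
| 76-90% | 12-26% | 0.06-0.17 |

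The share kept agrees with 1 - p. Simulated power is somewhat better than the formula in the middle of the range (0.50-0.59 against 0.41 at 50%). The whole-stay maximum varies less than Y alone (SD 0.83 to 0.95 there), and slightly more than 1 - p of the effect survives when d is not tiny. In every case the observed difference is no larger than the true one.

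**The case against.** The strongest reply is that the size is unknown. The protocol gives neither the timing of urea or creatinine peaks nor the postnatal age at either randomisation. A reader might infer that these values usually peak in the first days of life, so that the endpoint is mostly a baseline measurement. That rests on general clinical expectation. The protocol does not support it, and p could be small enough for the loss to be negligible. This stands, and it is why only a range is given.

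A reader might also infer that the comparison is biased in the sense of showing a difference that is not there. It is not. Randomisation balances pre-randomisation values in expectation, so what is lost is sensitivity. These maxima are one secondary item among many, outside the key safety outcomes named in sections 7.3 and 7.7. The primary analysis is untouched, and neurodevelopment, the main worry in section 1.5.3, is assessed directly at two years. All of this stands and limits the weight of the point.

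It can be said that eCRF detail is left to a study manual and that a statistical analysis plan, not shown here, will follow. That answers only in part. The whole-stay window is a stated rule in two sections, and if the eCRF holds one undated highest value, no later plan can separate earlier from later peaks.

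Two extensions should not be made. The endpoint "Age in days to achieve an enteral intake of 150 ml/kg/day" might seem to share the fault. Age in days is, however, a coherent measure, and babies enter randomisation 2 on 60-120 ml/kg/day of human milk. The protocol gives no frequency for babies who reach 150 ml/kg/day before randomisation 1. Second, creatine in sections 2.4.2 and 5.8 might be read as a different analyte. Sections 5.5 and 9.5 print creatinine, and 9.5 links it to renal function, so this is a spelling slip.

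**Conclusion.** The point holds as a fault of definition with a cheap remedy. As written, results that the allocated feed cannot have affected count as outcomes, contrary to the protocol's own practice for safety reporting and costs. The consequence is dilution to about (1-p) of a true effect: negligible for p below about 10%, about half lost at 50%, most lost at 80% or more. The direction and the formula follow from the definition and assume a common, small shift in the later maximum. The power figures rest in addition on an assumed effect of 0.15 SD. The value of p is not in the protocol and may differ by analyte and by randomisation.

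The exposure matters most for urea and creatinine in randomisation 2. A null result there, on the present definition, would be weaker evidence of safety than it appears.

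**What to change.** 1. In sections 2.4.2, 5.5, 5.8 and 9.5, define each endpoint as the highest value from the relevant randomisation to discharge or death, separately for randomisations 1 and 2.
2. In the eCRF, record the highest value since each randomisation with its date. A co-enrolled baby needs two entries only if the highest value since randomisation 1 came before randomisation 2. A date added to the whole-stay maximum would not be enough: it would identify the affected babies without supplying their later maximum.
3. Record the last value before each randomisation where one exists, and use it as a baseline covariate.
4. Print creatinine throughout.

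All values come from routine results, so no extra blood is taken. The cost is slightly more data entry, and some babies will have no later test. One weakness remains under either definition. A maximum tends to rise with the number of tests, and in an open-label trial clinicians may test more often in one arm. The report should say so when these endpoints are interpreted.

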5.9 Incidental findings

Incidental findings relate only to the MRI scans.

All MRI scans are acquired using a brain optimised research scanner within a tight quality-controlled environment at Edinburgh Imaging. Neuroimaging data will be obtained by brain research radiographers and subject to Edinburgh Imaging Quality Control procedures. Structural MRI data are reported according to a structured report by a paediatric radiologist, including incidental findings (29). We will notify the child’s general practitioner of any incidental findings that

Title: COLLABORATE	EDGE No: 181495	Sponsor: Imperial College London	Version: 3.0; 09/01/2026
---------------------------	---------------------------	--	---------------------------------

may be clinically actionable and any relevant NHS services that have been involved, through the clinical care team.

5.10 Permanent discontinuation of study interventions

Participant parents/guardians may discontinue study interventions by request. The attending clinician may discontinue participation if it is considered, following discussion with the Chief Investigator or authorised delegate, that the participant's health would be compromised by continuation. The reason for discontinuation will be recorded in the eCRF and medical records. Participants may also discontinue study interventions if the funder, sponsor or independent committees request this.

The participants will continue to be followed up even if the intervention has been discontinued

5.11 Withdrawal from the study

Withdrawal from the study refers to withdrawal from all study treatment and study procedures and can occur for the following reasons:

- Participant's parent or legal guardian's decision
- Participant is lost to follow-up
- Investigator's decision

As specified in the Parent Information Leaflet, should the parent/legal guardian withdraw consent for their baby's participation, data already available in the NNRD will be utilised.

6 SAFETY REPORTING

6.1 Adverse Events (AE)

An AE is any untoward medical occurrence in a clinical trial participant. An AE can therefore be any unfavourable and unintended sign (including an abnormal laboratory finding), whether or not considered related to the trial protocol.

6.2 Serious Adverse Events (SAE)

An SAE is defined as any event that

- Results in death
- Is life-threatening*
- Requires prolongation of hospitalisation**
- Results in persistent or significant disability or incapacity

* "Life-threatening" in the definition of "serious" refers to an event in which the participant was at risk of death at the time of the event; it does not refer to an event which hypothetically might have caused death if it were more severe.

** "Hospitalisation" means any extension of hospitalisation; it does not apply to scheduled admissions that were planned before study inclusion or visits to casualty (without admission).

Medical judgement will be exercised in deciding whether an adverse event/reaction is serious. Important adverse events/reactions that are not immediately life-threatening, or do not result in death or hospitalisation but may jeopardise a participant or may require intervention to prevent one of the other outcomes listed in the definition above should also be considered serious.

Title: COLLABORATE	EDGE No: 181495	Sponsor: Imperial College London	Version: 3.0; 09/01/2026
---------------------------	---------------------------	--	---------------------------------

6.3 Adverse Reactions (AR)

All untoward and unintended responses to the study intervention. All AE judged by either the reporting investigator or the sponsor as having reasonable causal relationship to the study intervention qualify as AR.

6.4 Serious Adverse Reactions (SAR)

A SAR is defined as a SAE that is judged to be related to any study intervention given to the participant.

6.5 Severity of adverse events

Mild:	Appears easily tolerated
Moderate:	Discomfort to cause interference with usual behaviour
Severe:	Not demonstrating usual activity

6.6 Causality of adverse events

The assignment of causality for AE should be made by the investigator or delegate responsible for the care of the participant using the definitions in the table below.

If any doubt about the causality exists, the local investigator should inform the study coordination centre who will notify the Chief Investigator. Other clinicians may be asked to advise. In the case of discrepant views on causality between the investigator and others, all parties will discuss the case.

Unrelated:	No evidence of any causal relationship
Unlikely:	Little evidence to suggest there is a causal relationship (e.g. the event did not occur within a reasonable time after the trial intervention). There is another reasonable explanation for the event (e.g. the participant's clinical condition, other concomitant treatment)
Possible:	There is some evidence to suggest a causal relationship (e.g. because the event occurs within a reasonable time after the trial intervention). However, the influence of other factors may have contributed to the event (e.g. the participant's clinical condition, other concomitant treatments)
Probable:	There is evidence to suggest a causal relationship and the influence of other factors is unlikely
Definite:	There is clear evidence to suggest a causal relationship and other possible contributing factors can be ruled out

6.7 Adverse reaction recording

The safety reporting window for this trial will be from randomisation (1 or 2) until 34 weeks PMA, discharge from neonatal care, or death, whichever is sooner. The reporting timelines are the same for infants participating in the mechanistic sub-study. Sites will be trained in safety reporting requirements.

Active monitoring of participants after the end of the trial is not required but if the investigator becomes aware of safety information that appears to be related to the trial, after a participant has completed the study, this should be reported to the Sponsor's delegate (ICTU) at [contact].

Title: COLLABORATE	EDGE No: 181495	Sponsor: Imperial College London	Version: 3.0; 09/01/2026
---------------------------	---------------------------	--	---------------------------------

6.8 Adverse reaction reporting

The use of pHDM, Preterm Formula and fortifier are established in routine care. In this extremely preterm population, we anticipate frequent foreseeable AE, SAE and AR, and a mortality rate to discharge from neonatal care of around 10%. For these reasons, AE, SAE, and AR will not be recorded.

All expected SAR have been listed as study endpoints, hence these events will be excluded from safety reporting. Any other SAR will be **unexpected** and extremely rare. These **unexpected** events will be reported to the Sponsor and Ethics Committee within 15 days of the investigator becoming aware of the event.

Cumulative data for safety endpoints (including expected SAR) will be included in regular safety reports reviewed by the Data Monitoring and Ethics Committee in accordance with the charter. Due to the established use of all trial interventions, additional safety oversight of expected events is not required.

Reporting of unexpected SAR will be performed through the eCRF. Unexpected SAR should be reported within 24 hours of the site study team becoming aware of the event as serious, unexpected and related (as described in section 6.4 and 6.6). SAR will be reported to the Sponsor's delegate (ICTU). Further details can be found in the safety reporting manual.

